difference which is in line with a weighted average effect size of mentoring programmes, based on comparisons of 18 studies in a meta-analysis of mentoring and offending using a random effects model (d=.21, 95% confidence interval .07 to .34) presented by Jolliffe and Farrington, 2008.³

Figure 2 presents the results of our power analysis at the protocol stage. It shows that in line with our conservative approach; we used a pre-test/post-test correlation of 0. This is because at the time we had no reason to believe based on data collected during the pilot trial that the variance would be different between the treatment and control group. However, we knew that inclusion of a pre-test as a covariate in impact analyses helps to explain (error) variance in the post-test and improves the likelihood of uncovering programme impacts by reducing the standard error of the impact estimate. It was difficult to estimate what the pre-test/post-test correlation would be as this depended on unknown sample characteristics and the characteristics of the measure under investigation (the SRDS when used in a sample similar to STEER, i.e., those who are known to have peers or family members involved in offending behaviour). The greater the estimated pre-test/post-test correlation the lower the MDES and the smaller the sample needed to detect this. In practice however, if the pre-test/post-test correlation changes from 0.0 to 0.4 the MDES for a sample size of 500 decreases from .25 to .23.

In line with good practice, we have conducted power analysis based on our final sample once all randomisation has been completed. This power analysis is based on the numbers involved in the trial at baseline. This is also presented in Figure 2. As part of this calculation, we have included a pre- post-test correlation of 0.5. This is based on values obtained from unpublished data from an RCT using the same outcome measure and in a similar population of adolescents (Humayun et al., 2019) which we discovered after our original power analysis for the protocol. It is also based on treating the SRDS variety score as a continuous variable in analysis as opposed to a dichotomous variable.

Our power analysis shows an MDES of 0.186 based on baseline data

SPSS 25 was used for calculations for the original protocol. PowerUp! (Dong, N. and Maynard, R. A., 2013) has been used for the calculations once all randomisation and baseline data had been completed.

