³ Please note that this rapid evidence assessment found that mentoring was more effective in reducing reoffending when contact between mentor and mentee was greater, in smaller scale studies, and when mentoring was combined with other services and interventions.

Figure 2: Sample size calculations

		Protocol	Randomisation
Minimum Detectable Effect Size (MDES)		0.19	0.186
Pre-test/ post-test correlations	Level 1 (participant)	0.0	0.5
	Level 2 (cluster)	N/A	N/A
Alpha		0.05	0.05
Power		0.8	0.8
One-sided or two-sided?		Two-sided	Two-sided
Number of participants by end of the trial	Intervention	327	337
	Control	327	349
	Total	654	686

Recruitment and baseline data collection was completed in October 2024. The cumulative T1 sample at the end of this period was 686.

337 young people were allocated to the intervention group, and 349 to the control group. This is broadly in line with the intended 1:1 allocation ratio. More information can be seen in Figure 3 below.

Referred into STEER = 1052 Eligible for STEER = Disengaged/became 997 ineligible= 316* Consented = Withdrew/excluded 694 from evaluation = 8 Baseline measures = 686 STEER= Signposting 337 = 349

Figure 3: Consort flow diagram for baseline data collection

Analysis

Overview

The following presents the analytical approach for the Efficacy Study. We currently do not know the structure of the complete data-set (for example, extent of or categories of missing data etc.) that we will receive as part of the Efficacy Study. This should be considered when interpreting the following analytical plan.

There is considerable debate about best practice when it comes to the analysis of data from RCTs. For example, Twisk et al. (2018) advocate for utilising longitudinal analysis of covariance or a repeated measures analysis without the treatment variable, but with the interaction between treatment and time in the model controlled. They argue that failure to control for baseline differences in outcomes between the groups can lead to biased estimates in the treatment. Alternatively, others have cautioned against this approach (e.g., Sen, 2013).

Based on our understanding of the literature our analysis will be conducted using General Linear Models controlling for baseline measurement of the outcome variable. An intention to treat approach will be used with all models unless otherwise stated. This in line with YEF Guidance (YEF, 2021).

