[•] These are young people who disengaged or became ineligible because they: refused the service, had a parent who refused the service, moved out of area, were uncontactable, had too many services involved, or were deemed too complex due to an escalation in risk following the acceptance of referral.

The primary outcome for the evaluation of STEER is a reduction in prevalence of self-reported offending behaviours between baseline and six months as measured by the SRDS variety score.

The secondary outcomes that we are investigating are that young people receiving STEER compared to the business as usual (control) group have (See Figure 1 for more information about measures):

- A positive relationship with their mentor.
- Improved pro-social values and behaviours.
- Improved emotional symptoms.
- Improved behaviours
- Positive relationships/role models.

The General Linear Model will include the appropriate baseline outcome measure and the treatment dummy variable. For example, for the analysis of the primary outcome measure (SRDS Variety Score) the baseline SRDS variety score measure will be included and whether the individual received STEER or not

The purpose of these analyses is to estimate the difference between the STEER arm and the business-as-usual arm for each of the primary and secondary outcomes.

Variable transformation

It is possible that the baseline and outcome variables may be skewed. Skew will be assessed using the traditional criteria based on their distribution (i.e., skews of greater or equal to 1.0 or less than or equal to -1.0). Arguably, it is more desirable to use a generalised liner model (GLM) for the appropriate modelling of non-normally distributed variables (e.g., Akram et al., 2023), than it is to transform the data.

The analytic approach has been developed a priori and will be conducted with SPSS.

The syntax for all analysis will be provided once it has been developed after all data has been collected.

Primary outcome analysis

The primary outcome is a reduction in offending measured by the SRDS Variety Score. All young people will have completed the SRDS questionnaire before randomisation and again at around six months post-randomisation.

The SRDS Variety Score is measured on a scale from 0-19 with 0 indicating the young person has not reported any of the 19 forms of delinquency/offending behaviour and a score of 19 indicating that they have undertaken all forms of delinquency/offending behaviour.

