We will be using a General Linear Model, repeated measures design (assuming normality) or a generalized linear model, repeated measures design if the SRDS Variety score is nonnormally distributed. We will include a treatment by outcome interaction term in the analysis.

This analysis is designed to evaluate the differences in SRDS Variety Score between those in STEER and those who received business as usual (i.e. the control group).

This analysis will be conducted in SPSS.

Secondary outcomes analysis

Our approach to analysis of secondary outcomes will mirror the approach outlined above for the analysis of the primary outcomes. The secondary outcomes are:

- A positive relationship between the young person and mentor measured by the Social Support and Rejection Scale (SSRS).
- Improved pro-social values and behaviours measured by the SDQ pro-social values subscale.
- Improved emotional symptoms measured by the SDQ emotional symptoms subscale.
- Improved behaviour measured by the SDQ conduct problems subscale.
- An increase in positive relationships/role models measured by the measured by the SDQ peer relationships problem subscale.

All SDQ subscales contain 5 items and are measured on scales from 0 to 10. For the prosocial values subscale high scores are desirable (e.g., greater prosocial values), but for the other subscales (e.g., emotional symptoms subscale, conduct problems subscale, peer relationship subscale) high scores are not desirable (e.g., greater emotional problems, greater conduct problems, poorer peer relationships).

The SSRS has 4 dimensions; 'Feels valued', 'Trust', 'Mentoring', and 'Negativity'. Each item is scored from 1 (never) to 5 (always). Each subscale score is the average of items that make up the subscale. Higher scores on the negativity scale reflect higher levels of stress and negativity within the relationship. For the overall scoring of the scale a high score represents a positive relationship.

We will be using general linear models, repeated measures design (assuming normality) or generalized linear models, repeated measures design if the particular subscale is non-normally distributed. This will be determined once all data has been collected. We will include a treatment by outcome interaction term in the analysis.

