A note on intra-cluster correlation

This is not a clustered randomised controlled trial. As such, we will not be calculating intraclass correlations.

Presentation of outcomes

The effect sizes will be calculated using Hedges' g, as specified in the following equation:

Hedges' $g = (x1 - x2) / \sqrt{(n1-1)*s12 + (n2-1)*s22} / (n1+n2-2)$

where:

x1, x2: The sample 1 mean and sample 2 mean, respectively

n1, n2: The sample 1 size and sample 2 size, respectively

s12, s22: The sample 1 variance and sample 2 variance, respectively

With a sample of greater than 20 there is limited difference with Cohen's d. However, if the standard deviations between the treatment and comparison group are different, we would

propose to use Glass' delta, which only uses the control group's standard deviation (Lipsey & Wilson, 2001).

The confidence interval for the Hedge's g statistic is:

 $g \pm \varphi - 1 (1-(\alpha/2))gse$

where:

 φ - 1 = the percent point function of the normal distribution

gse= the standard error of the g statistic

 $= V(n1+n2)/n1n2 + g^2/2(n1+n2)$

References

Dong, N. and Maynard, R. A. (2013). *PowerUp!*: A tool for calculating minimum detectable effect sizes and sample size requirements for experimental and quasi-experimental designs. *Journal of Research on Educational Effectiveness*, *6*(1), 24-67. doi: 10.1080/19345747.2012.673143

Goodman, R., 2005. *The Strengths and Difficulties Questionnaire*. Available at: https://www.sdqinfo.org/a0.html [Accessed 17/8/23].

Karcher, M.J. and Nakkula, M.J., 2010. Youth mentoring with a balanced focus, shared purposes, and collaborative interactions. *New Directions for Youth Development* 2010(126), pp.1-32.

Lipsey, M. and Wilson, D. (2021) Practical meta-analysis. Thousand Oaks, CA: Sage.

Roffman, J. G., Pagano, M. E., and Hirsch, B. J., 2000. *Social support and rejection scale*. Evanston, IL: Human Development and Social Policy, Northwestern University.

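### The SAP's Hedges' g and its interval are not tied to the baseline-adjusted model, so the reported effect size is valid but less precise than the planned analysis and can disagree with it about zero

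*SAP*

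**What the plan says.** **Effect size (SAP, Presentation of outcomes).** "The effect sizes will be calculated using Hedges' g, as specified in the following equation". The terms are then defined: "x1, x2: The sample 1 mean and sample 2 mean, respectively" and "s12, s22: The sample 1 variance and sample 2 variance, respectively". The interval is g plus or minus a normal quantile times a standard error ("gse= the standard error of the g statistic") that contains only n1, n2 and g. No adjusted mean, model coefficient, model standard error or pre/post correlation enters. The section does not say whether the means are follow-up or change means. It allows a switch to Glass' delta if the arm SDs differ.

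**Model (SAP, Analysis, Overview).** "our analysis will be conducted using General Linear Models controlling for baseline measurement of the outcome variable", with the terms named as follows: "The General Linear Model will include the appropriate baseline outcome measure and the treatment dummy variable".

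**Model (SAP, Primary outcome analysis).** "We will be using a General Linear Model, repeated measures design (assuming normality) or a generalized linear model, repeated measures design", the second option applying if the score is not normally distributed, with an interaction term added. The secondary outcomes follow the same approach.

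**Power (SAP, Sample size calculations).** The reason given for a baseline covariate is that "inclusion of a pre-test as a covariate in impact analyses helps to explain (error) variance in the post-test". Figure 2 gives an MDES of 0.186 at randomisation, with a correlation of 0.5, two-sided alpha 0.05, power 0.8, and 337 and 349 participants.

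**The concern.** The plan estimates the arm difference in one way and presents it in another, and no rule connects the two. Each outcome could carry a test from a baseline-adjusted model beside a standardised effect and interval from an unadjusted two-sample comparison. The two can differ in size and in whether zero is excluded, and the SAP does not say which one the reader should rely on. The printed interval would also be wider than the precision behind the 0.186. The choice is best fixed before results are known, and the SAP says the analysis syntax is still to be written.

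**Working it through.** **Inputs.** n1 = 337, n2 = 349, N = 686, r = 0.5, alpha 0.05 two-sided, power 0.80 (SAP Figure 2). Both scores are taken as normal with SD 1, with no attrition. The means in g are read as follow-up means. The printed formulas are read with the brackets that their layout implies; missing brackets may come from text extraction and are not counted.

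**1. The plan's own MDES.** MDES = (t0.975 + t0.80) × √[(1 − r²) × N/(n1 × n2)], 683 degrees of freedom.
- N/(n1 × n2) = 686/117,613 = 0.005833, square root 0.0764.
- r = 0.5: 0.1856, which rounds to the stated 0.186.
- r = 0: 0.214.

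So the stated figure requires the baseline adjustment.

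**2. Width under the baseline-covariate model.**
- SAP formula at g = 0.186: √(0.005833 + 0.186²/1372) = 0.0765; × 1.96 = 0.150.
- Adjusted: 0.0764 × √0.75 = 0.0661; × 1.96 = 0.130.
- Ratio: 1/√0.75 = 1.15.

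The ratio depends on r and not on n, so attrition widens both intervals alike:

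| r | Adjusted MDES | Adjusted half-width | Raw g interval wider by |
|---|---|---|---|
| 0.4 | 0.196 | 0.150 × √0.84 = 0.137 | about 9% |
| 0.5 | 0.186 | 0.130 | about 15% |
| 0.6 | 0.171 | 0.150 × √0.64 = 0.120 | 25% |

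**3. Chance of excluding zero at a true effect of 0.186.**
- g interval: Φ(0.186/0.0765 − 1.96) = 0.68.
- Model: Φ(0.186/0.0661 − 1.96) = 0.80.

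If the two point estimates happened to coincide, any value from about 0.13 to 0.15 would be significant in the model while the SAP interval included zero. At 0.14 the SAP formula gives −0.010 to 0.290, and the adjusted version 0.010 to 0.270.

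**4. Simulation (20,000 trials per effect, bivariate normal, r = 0.5).**
- True effect 0.186: model only 14.2%, g only 2.2%; they disagree in about 16%.
- No effect: g excludes zero in 4.9% of trials and the model in 5.0%; they disagree in about 4.6%.

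**5. Where the lost precision comes from.** Raw g differs from the adjusted estimate by r times the chance baseline difference, with SD 0.5 × 0.0764 = 0.038. Since √(0.0661² + 0.038²) ≈ 0.076, this noise is the whole gap between the two standard errors. It is not a further loss on top of the wider interval.

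**6. The repeated measures reading.** If the interaction in Primary outcome analysis is taken as treatment by time, the contrast is the difference in change. Its variance factor is 2(1 − r), which equals 1 at r = 0.5, so its standard error is about that of raw g (0.0764). There is then no width difference at that r. The point estimates differ by the baseline mean difference, and in the simulation at 0.186 the two conclusions disagree in about 29% of trials.

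**The case against.** The strongest reply is that nothing invalid is planned. Under randomisation raw g is unbiased. Its interval has about nominal coverage, as the 4.9% under no effect shows. Disagreement at the MDES is mostly conservative, with the model significant and the interval for g spanning zero. The model remains the analysis that estimates and tests the arm difference, g is a standardised metric beside it, and the 0.186 describes the model-based test whatever else is printed. All of this stands.

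Two further parts of the reply also stand. The width and power figures apply only to the baseline-covariate model, not to the repeated measures contrast. And the correlation of 0.5 comes from another trial's unpublished data, so the size is uncertain.

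Three stronger readings are tempting but not supported:
- A reader might infer that g is the headline result and replaces the model estimate. The SAP does not say so; it only defines no other effect size with an interval.
- A reader might infer that chance baseline imbalance biases g in a way its interval misses. It does not: step 5 shows that the wider interval already contains that noise.
- A reader might infer that the 0.186 is wrong. It reproduces for the model it describes.

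The reply does not remove the missing link. No sentence ties g to either model, labels it descriptive, or says which result governs if they differ.

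**Conclusion.** The inconsistency is real. It concerns efficiency and coherence of reporting, not bias or type I error. Under the baseline-covariate model with 337 and 349 analysed and r = 0.5, the interval for g is about 15% wider than the planned analysis supports (about 9% at r = 0.4, 25% at r = 0.6). At a true effect of 0.186 it excludes zero in about 68% of trials against 80%, and the two results disagree about zero in about 16%. These figures assume normal scores and full follow-up. Under the repeated measures contrast at r = 0.5 the widths are about equal and the conflict is in the point estimates. The problem affects the primary outcome and the SDQ subscales. It does not arise in this form for the SSRS, for which Figure 1 lists no baseline.

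**What to change.** 1. Reconcile Analysis, Overview with Primary outcome analysis (and the matching text for secondary outcomes) on the baseline-covariate model.
2. In Presentation of outcomes, take the numerator of g from that model's adjusted treatment contrast. Divide it by the pooled unadjusted SD, or by the control-group SD if Glass' delta is used. Obtain the interval by dividing the model's confidence limits by the same SD.
3. If a generalized linear model is used, its coefficient may not be a mean difference. Use the model-based marginal difference in mean score, with a delta-method or bootstrap interval, and standardise that.
4. Report the adjusted difference in SRDS points with its 95% interval. Label raw means, SDs and any raw g as descriptive.
5. For the SSRS, with no baseline listed in Figure 1, the unadjusted g stands.

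The cost is minor rewording in these sections and some extra syntax, slightly more in the generalized branch. No new data are needed.
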